9.1.2 Imputation

Unless otherwise noted, data will not be imputed.

9.1.3 Descriptive Statistics

Unless otherwise indicated, continuous variables will be summarized with the following descriptive statistics:

- n (number of observations),
- (arithmetic) mean,
- standard deviation (SD),
- minimum (min) value,
- median, and
- maximum (max) value.

Categorical data will be summarized with frequencies and percentages. Percentages by categories will be based on the number of subjects exposed within a treatment.

For categorical data the categories will be presented in the tables exactly as they appear in the eCRF / Database.

9.1.4 Pooling

Summary statistics will be calculated by treatment (and time point, if applicable). Placebo data will be pooled for Parts A (SAD) and B (MAD). Placebo data from the periods under fed conditions (i.e. Period 2 for Cohorts 3 and 4) will be pooled and reported as separated treatment.

9.1.5 Unscheduled Measurements

Unscheduled measurements will be included in the listings. Except for unscheduled measurements used for baseline, unscheduled measurements will be excluded from the descriptive statistics and statistical analysis.

9.2 Analysis Data Definitions

9.2.1 Baseline Definition

Unless otherwise stated, baseline for post-dose evaluations is defined as the last observation recorded before the first study drug administration in each period. The last observation can be an unscheduled / repeated measurement.

9.2.2 Treatment/Subject Grouping

In summary tables, data will be presented by study part and treatment.

Table 3 Part, Cohort and Treatment Labels

Label	Grouping
Study Part	Part A (SAD) Part B (MAD)
Cohorts	Part A: 1-6 and 10 Part B: 7-9
Planned Treatments	Part A (SAD): – Placebo – Placebo fed – 10 mg LY – 50 mg LY – 100 mg LY – 30 mg LY fed – 200 mg LY – 200 mg LY fed – 300 mg LY – 100 mg LY fed (-30 min) – 100 mg LY fed (+30 min) – 100 mg LY fed (+60 min) Part B (MAD): – Placebo QD – 30 mg LY QD – 60 mg LY QD – 100 mg LY QD

LY = LY 3526318; QD = once daily

For subjects for which the actual treatment received does not match the planned treatment, the treatment actually received will be used for the analysis, in any summaries or analysis. In case this leads the number of subjects receiving those actual treatments being less than 2, the data for these subjects will only be listed and not included in any summaries or analyses.

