10.0 Analysis Sets

Analyses	Randomized Set	Safety Set	Pharmacokinetic Set
Disposition Summaries	✓		
Safety Assessments		✓	
Baseline Characteristics		✓	
Primary Analysis		✓	
PK Concentrations			✓
PK Parameters			✓

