10.2 Safety Set

The safety set will consist of subjects who receive at least one dose of study drug (LY3526318 or placebo). This set will be used for the safety data summaries, baseline characteristic summaries, and PK concentration summaries.

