18.1.1 Adverse Events

Treatment-emergent adverse events (TEAE) are those which occur after the first dose of study drug.

All AEs (including non-treatment-emergent events) will be listed, including the AE description (verbatim term), Medical Dictionary for Regulatory Activities (MedDRA) system organ class (SOC) and preferred term (PT), start date and time, end date and time, severity, relation to study drug, seriousness, action taken, and outcome.

All AE summaries will include only TEAE. All TEAEs occurring following dosing will be attributed to the treatment that was received.

A breakdown of the number of TEAEs, and the number and percentage of subjects reporting each TEAE, categorized by system organ class and preferred term coded according to MedDRA (Version 22.1), will be presented by treatment and overall for each study part. One table is presented for all TEAEs and one table is presented for TEAEs considered to be related to the study medication. Subjects will only be counted once within each SOC or PT per treatment.

Additionally, a summary table with TEAEs by severity and relationship to study drug will be presented by study part and treatment.

The following missing data will be imputed as defined (for calculations only / will not be presented):

- Missing AE start and / or end times for the calculation of onset and duration will be assumed to be at 00:01 for a start time and 23:59 for end times
- Missing AE severity or relationship will be assumed to be severe or related, respectively
- Missing AE start times for the determination of treatment emergence will be assumed to occur after treatment unless partial date documents the AE as happening prior to treatment
- Missing AE start times for the determination of treatment assignment will be assumed to occur after treatment on the recorded date
- Missing AE start date will be assumed to be after treatment for the determination of TEAE and on treatment

For the US Clinical Trials Registry (CTR), a CTRAE summary table and the CTRAESUMM SAS dataset will be provided separately from the TFL created for CSR. The table and corresponding dataset will be created according to the specifications provided by the Sponsor.

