Figure 14.2.2.4	Geometric Mean LSN3528305 Plasma Concentrations Versus Time by Day and Treatment (Linear Scale and Semi-Logarithmic Scale)	PK
Figure 14.2.2.5	Geometric Mean LY3526318 Trough Plasma Concentrations Versus Time by Treatment (Linear Scale Scale)	PK
Figure 14.2.2.6	Combined Individual LY3526318 Plasma Concentrations versus Time by Treatment and Day (Linear Scale and Semi-Logarithmic Scale)	SAF
Figure 14.2.2.7	Combined Individual LSN3528305 Plasma Concentrations versus Time by Treatment and Day (Linear Scale and Semi-Logarithmic Scale)	SAF
Figure 14.2.2.8	Individual LY3526318 Plasma Concentrations versus Time by Subject (Linear Scale and Semi-Logarithmic Scale)	SAF
Figure 14.2.2.9	Individual LSN3528305 Plasma Concentrations versus Time by Subject (Linear Scale and Semi-Logarithmic Scale)	SAF
Table 14.2.2.10	Individual Values and Descriptive Statistics of LY3526318 PK Parameters by Treatment	PK
Table 14.2.2.11	Individual Values and Descriptive Statistics of LSN3528305 PK Parameters by Treatment	PK
Table 14.2.2.12	Exploratory Statistical Analysis of Dose Proportionality	PK

Section 14.3 Safety Data

Section 14.3.1 Adverse Events

Table 14.3.1.1	Summary of All Treatment-Emergent Adverse Events by System Organ Class and Preferred Term	SAF
Table 14.3.1.2	Summary of Related Treatment-Emergent Adverse Events by System Organ Class and Preferred Term	SAF
Table 14.3.1.3	Summary of Treatment-Emergent Adverse Event by Treatment, Relationship and Severity	SAF

Section 14.3.2 Listing Deaths and Other Serious Adverse Events (If applicable)

Table 14.3.2	Listing of Deaths and Other Serious Adverse Events	SAF
Section 14.3.3 Narratives of Deaths, Other Serious and Significant Adverse Events (Not Applicable)		
Table 14.3.3	Not part of TFL – Reserved for Narratives in CSR	
Section 14.3.4 Clinical Laboratory Data		
Table 14.3.4.1	Summary of Clinical Laboratory Data - Clinical Chemistry	SAF
Table 14.3.4.2	Summary of Clinical Laboratory Data - Hematology	SAF
Table 14.3.4.3	Listing of Abnormal Laboratory Values	SAF
Section 14.3.5 Other Safety Parameters		
Table 14.3.5.1	Summary of Vital Signs	SAF
Table 14.3.5.2	Summary of 12-Lead Electrocardiogram	SAF
Figure 14.3.5.3	Scatter Plots of QTcF Versus Plasma Concentrations of LY3526318	SAF

Table 10 List of Subject Data Listings

Output	Title
Section 16.2.1 Disposition	
Listing 16.2.1.1	Subject Disposition
Section 16.2.2 Protocol Deviations	
Listing 16.2.2.1	Not part of TFL – Reserved for protocol deviations in CSR

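### Minor, and only if triggered: the fewer-than-2 rule in SAP 9.2.2 has no safety exception, so an overall TEAE count labelled for the Safety Set could omit a dosed subject or that subject's events

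*SAP*

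**What the plan says.** SAP 9.2.2 (Treatment/Subject Grouping) uses the actual treatment wherever it differs from the planned one. It then adds a small-number rule. Its condition reads "In case this leads the number of subjects receiving those actual treatments being less than 2". When that condition is met, the stated consequence is that "the data for these subjects will only be listed and not included in any summaries or analyses".

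The safety sections read differently:

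- SAP 10.2: "The safety set will consist of subjects who receive at least one dose of study drug", whether active or placebo. "This set will be used for the safety data summaries", among other uses.
- SAP 10.0: the row "Primary Analysis" is ticked for the Safety Set. Section 9.2.4.1 names AEs and SAEs as the primary endpoint.
- SAP 18.1.1: TEAE counts, and numbers and percentages of subjects, "will be presented by treatment and overall for each study part".
- SAP Appendix 3, Table 9: Table 14.3.1.1, "Summary of All Treatment-Emergent Adverse Events by System Organ Class and Preferred Term", carries the population label SAF.

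**The concern.** A subject who receives an off-plan treatment has been dosed and so belongs to the Safety Set. If no one else received that treatment, 9.2.2 read literally takes the subject's data out of every summary, including the overall TEAE presentation. That presentation is labelled as covering all dosed subjects.

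At stake is the completeness of a descriptive summary of the primary endpoint, for a subject whose dosing departed from plan. Two programmers could each follow the SAP and reach different overall counts. In a single-period cohort, the analysis-set counts planned in SAP 11.0 would show the full Safety Set, while the overall TEAE column would be one subject short with no planned explanation.

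**Working it through.** **Setting the passages side by side**

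1. Membership: one dose is enough for the Safety Set (10.2). An off-plan dose counts.
2. Use: the safety summaries and the primary analysis run on that set (10.0, 10.2), and the overall TEAE presentation is one of them (18.1.1; Appendix 3, Table 9).
3. Exclusion: 9.2.2 removes the subject's data from any summary when fewer than 2 subjects received the treatment.
4. Precedence: none is stated. Sections 9.1.2, 9.1.3 and 9.2.1 each open with wording that lets another section override them. Section 9.2.2 has no such wording, and neither 10.2 nor 18.1 exempts safety data.

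The conflict is therefore between 9.2.2 on one side and the Safety Set definition and overall presentation on the other.

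**Denominators**

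Inputs are the planned cohort sizes in SAP 6.1 and the 6.2 table, with Cohort 3 at 8 after the decision not to dose males, and no replacements.

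- Plan's own figures: Part A = 6 × 8 + 12 = 60 and Part B = 3 × 8 = 24. Both match SAP 6.1.
- Part A after the Cohort 3 change: 7 × 8 = 56. Single-period Cohorts 1, 2, 5 and 6 give 4 × 8 = 32; multi-period Cohorts 3, 4 and 10 give 3 × 8 = 24.
- LY3526318 only: Part A = 6 × 6 + 8 = 44; Part B = 3 × 6 = 18.

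**Effect on an event seen only in the affected subject** (percentages as integers, per SAP 9.1.1)

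| Case | Subject counted | Rule applied |
|---|---|---|
| Part A, single-period cohort, placebo included | 1/56 = 1.79% (2%) | 0/55 |
| Part B, placebo included | 1/24 = 4.17% (4%) | 0/23 |
| Part A, single-period cohort, LY3526318 only | 1/44 = 2.27% (2%) | 0/43 |
| Part B, LY3526318 only | 1/18 = 5.56% (6%) | 0/17 |
| Cohorts 3, 4, 10, rule read by period, placebo included | 1/56 (2%) | 0/56 |
| Cohorts 3, 4, 10, rule read by subject, placebo included | 1/56 (2%) | 0/55 |

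The SAP does not say whether overall includes placebo, so both versions are shown. In the multi-period cohorts 9.2.2 does not say whether one period or all of a subject's periods are removed. The per-period baseline in 9.2.1 fits the first reading: the subject stays in N but the event is lost. On the second reading 2 subject-periods (Cohorts 3 and 4) or 3 (Cohort 10) are lost instead of 1.

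**The case against.** The best defence is context. Section 9.2.2 is about grouping, it opens with presentation by part and treatment, and its Table 3 has no overall group. On that view the rule only says what to do with a group of one and leaves the Safety Set alone. This is probably what was meant, but the wording covers any summary or analysis, so the text does not secure it.

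The other points limit the size of the problem:

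- The trigger is remote. It needs a dosing error that creates a treatment received by one subject only. Trained unit staff give the doses, with mouth and hand checks (Protocol 7.2.1, 7.6). A swap to an existing treatment would not normally meet the condition, and the adjusted doses in SAP 6.2 are planned changes.
- The information survives elsewhere: all AEs, deaths and SAEs are listed (SAP 18.1.1, 18.1.2), deviations are reported in the CSR (12.0), and Appendix 3 lists analysis sets, drug administration and AEs leading to withdrawal.
- Protocol 10.3.1 asks for summaries by dose level and pooled placebo, not for an overall column. No TEAE table shell is given.
- There is no hypothesis testing (SAP 9.4.3).

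All of this stands. None of it restores the subject to the overall count labelled SAF.

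Three stronger readings are tempting, and the documents do not support them:

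- A reader might infer that 9.2.2 also conflicts with the attribution rule in 18.1.1, "All TEAEs occurring following dosing will be attributed to the treatment that was received". It does not: both sections are as-treated. Only the overall presentation conflicts.
- A reader might infer that the overall denominator is undefined, because SAP 9.1.3 bases percentages on subjects exposed within a treatment. The SAF label together with 10.2 supplies it.
- A reader might blame the rule for shrinking a six-subject active arm to five. The as-treated principle moves the subject out of the planned arm anyway.

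**Conclusion.** The point holds as a minor, conditional inconsistency. If one subject alone receives an off-plan treatment, 9.2.2 followed literally makes the overall summary of the primary endpoint incomplete for the Safety Set it is labelled with. The size is one subject, or one subject's events, in a descriptive count. The figures assume planned cohort sizes after the Cohort 3 change, no replacements (SAP 6.2 allows them) and a single affected subject. If no one receives a unique off-plan treatment there is no effect, and nothing in the documents shows that anyone did. By-treatment summaries are affected only in that a one-subject treatment gets no column.

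**What to change.** Amend SAP 9.2.2 so that the fewer-than-2 rule suppresses only the separate by-treatment column and the PK and statistical analyses, and only for the affected period. State that every Safety Set member and all their TEAEs count in the overall TEAE column, with the Safety Set N for that study part as denominator. Add a table footnote giving the treatment actually received and noting that it has no column of its own. Cross-refer from 10.2 and 18.1.1, and say there whether overall includes placebo.

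The cost is a short amendment to 9.2.2, two cross-references and a footnote. The one downside is that an event may appear in the overall column and under no treatment column, which the footnote explains. SAP 3.0 requires an approved SAP before database lock and unblinding, so the change is best made before then.

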9.2.3 Common Variable Derivations

Table 4 Common Variable Derivations

Variable	Definition/Calculation	Variable Name*
Change from Baseline	Post-dose Observation minus Baseline Observation	CHG
Analysis Study Day	Prior to first day of dosing: Date of Measurement minus Dose Date On or after first day of dosing: Date of Measurement minus Dose Date +1	ADY
Scheduled time	Planned time of the assessment. Time in hours of the assessment relative to the planned time of the first drug administration per period.	ATPT/ATPTN
Actual Time	Actual time in hours calculated as the sampling data/time minus the date/time of the first drug administration per period.	ARELTM

*) CDISC ADaM defined variable name.

9.2.4 QC

The ADaM compliant analysis datasets and the TFLs will be QC'd according to the general PRA EDS QC plan.

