7.2.1 Selection and Timing of Doses

In Part A, the single dose of the study drug will be administered at the CRU approximately between 08:00 AM and 11:00 AM.

In Part B, all doses will be administered at the CRU approximately between 08:00 AM and 11:00 AM.

A trained CRU personnel member will administer all doses of the study drug at the CRU.

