6.2 Randomization

A randomization schedule was generated by the EDS Biostatistics department of PRA for all cohorts except Cohort 10 according to the study specific Randomization Specifications created by then PRA biostatistician and approved by the Sponsor.

Part	Cohort	Period	Planned Treatment [#]	Actual Dose [#]	♀	♂	Stratified by sex
A	1a (sentinel)	1	10 mg LY3526318 or Placebo	10 mg	2		No
	1b	1	10 mg LY3526318 or Placebo	10 mg	6		No
	2	1	50 mg LY3526318 or Placebo	50 mg	4	4	Yes
	3	1	100 mg LY3526318 or Placebo	100 mg	8	4*	Yes
		2	100 mg LY3526318 or Placebo fed	30 mg	8		NA
	4	1	400 mg LY3526318 or Placebo	200 mg	8		NA
		2	400 mg LY3526318 or Placebo fed	200 mg	8		NA
	5	1	800 mg LY3526318 or Placebo	300 mg	8		NA
	6	1	1000 mg LY3526318 or Placebo	30 mg	8		NA
	10 (additional)	1	100 mg LY3526318 Fed standardized high fat meal to start 30 minutes prior to dose administration	100 mg	8		NA
		2	Fasted at least 8 hours predose with a standardized high fat meal administered 30 minutes post dose	100 mg			
		3	Fasted at least 8 hours predose with a standardized high fat meal administered 1 hour post dose	100 mg			
	11 (additional)	1	TBD mg LY3526318 or Placebo	NA	8		NA
B	7	1	100 mg LY3526318 or Placebo QD	30 mg	8		NA
	8	1	400 mg LY3526318 or Placebo QD	60 mg	8		NA
	9	1	Up to 1000 mg LY3526318 or Placebo QD	100 mg	8		NA
	12 (additional)	1	TBD mg LY3526318 or Placebo QD	NA	8		NA
	13 (additional)	1	TBD mg LY3526318 or Placebo QD	NA	8		NA
*) Doses may be adjusted based on data obtained in previous study cohorts, see actual dose column for the adjusted doses.							
*) As a result of exposures found in the interim PK data after Cohort 2 being higher than expected, it was decided not to dose male subjects with a 100 mg dose in Cohort 3 and therefore the number of subject in this cohort was also 8.							
NA=not applicable, TBD=to be determined.							

Replacement subjects will receive the same randomization number as the subject to be replaced increased by 1000 and will be administered the same.

In Cohorts 3 and 4 the female subjects will be dosed in a 2nd period in which they were to receive the same treatment under fed conditions. After evaluation of the interim PK results, it was decided to reduce the dose level of Period 2 for Cohort 3 to 30 mg under fed conditions.

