16.2 Pharmacokinetic Summaries

16.2.1 Pharmacokinetic Concentrations

Plasma concentrations for LY3526318 below the quantifiable limit (BQL) will be set to $\frac{1}{2}$ lower limit of quantification (LLOQ) in the computation of descriptive statistics of concentration values. Descriptive statistics (number of subjects, arithmetic mean, standard deviation, coefficient of variation, median, minimum, maximum, geometric mean, and geometric CV) will be used to summarize the plasma concentrations by treatment at each scheduled time point. If over $\frac{1}{2}$ the subjects in a given cell have values BQL then the descriptive statistics will not be presented and will instead display as BQL for the mean and minimum. All other statistics except the maximum will be missing.

Linear and semi-logarithmic plots of the geometric mean plasma concentration versus scheduled sampling time will be presented by part showing all fasted treatments in a single figure.

Separate geometric mean linear and semi-logarithmic plots will show the effect of food given at the same dose (fed versus fasted) for the 30 mg and 200 mg cohorts, that is: Cohort 3 Period 2 and Cohort 6 Period 1 for 30 mg and Cohort 4 Periods 1 and 2 for 200 mg. Also separate geometric mean linear and semi-logarithmic plots will show the effect of food and the timing of food given at the 100 mg dose level (predose, 30 min postdose and 1 hour postpose and fasted) from Cohort 10 Periods 1-3 and Cohort 3 Period 1, respectively. These plots will show time in hours. The plots will match the summary table results and will not have an observation at a given time point if more than half of the subjects have values BQL.

For the multiple dose part, geometric mean profiles will be presented for all treatments in a single plot with a Day 1 and Day 14 profiles superimposed. In addition, linear geometric mean through plasma concentrations versus scheduled sampling time will be presented. These trough plots will include all trough concentrations from time zero on Day 1 up to 24 hours after dosing on Day 14.

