16.2.2 Pharmacokinetic Parameters

Plasma PK parameters for LY3526318 will be estimated using non-compartmental methods with WNL.

The plasma PK parameters will be estimated from individual concentration-time data. In estimating the PK parameters, BQL values at the beginning of the profile will be set to zero. BQL values that occur after the first quantifiable point will be considered missing. Values that are embedded between BQLs, or quantifiable values occurring after two or more BQLs, will be set to missing at the discretion of the pharmacokineticist. Actual sampling times will be used in all computations involving sampling times. If the actual time or dose time is missing, the scheduled time may be substituted in order to calculate the PK parameter.

The points to be included in the λz range will be determined by the pharmacokineticist after inspection of the semi-log concentration-time profiles. At least 3 points will be required to be used. The C_{max} data point will not be included.

Descriptive statistics (number of subjects, arithmetic mean, geometric mean, standard deviation, arithmetic and geometric CV, median, minimum, and maximum) will be used to summarize the calculated plasma PK parameters by treatment. For T_{max} , only median, min and max will be presented.

Urine PK parameters will be derived in SAS. Descriptive statistics (number of subjects, arithmetic mean, geometric mean, standard deviation, arithmetic and geometric CV median, minimum, and maximum) will be used to summarize the calculated urine PK parameters by treatment.

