^a Participants who discontinue from the study prior to study completion should complete the ED visit procedures.

^b Screening will be performed within 28 days of first dose administration.

^c Vital signs and temperature should be measured at following time points: Days 1 and 14 – predose and 2 hours, 4 hours, and 8 hours postdose; predose on all other indicated dosing days.

^d Hematology and chemistry sample should be collected predose on stipulated visits.

^e A standard urine test strip/dipstick may be used.

^f A serum beta-hCG test will be performed in all female participants, except in female participants with confirmed hysterectomy.

^g A single 12-lead ECG will be recorded in the supine position after 5 minutes of rest at following time points: Days 1 and 14 – predose and 2 hours, 4 hours, and 8 hours postdose.

^h Study drug will be administered once daily in the CRU through Day 14, and the exact time of administration will be recorded. All doses are planned to be administered in a fasting state; however, following a review of the food effect data from Part A, all doses may be administered with food. Fasting on PK sampling days is defined as at least 8 hours predose and 4 hours postdose. Fasting on non-PK and predose only PK sampling days is defined as at least 8 hours predose and 2 hours postdose on all other indicated days.

- ⁱ On Days 1 and Day 14, PK samples will be collected at time zero (predose) and at approximately at 1, 2, 4, 6, 8, and 12 hours after dosing. On Day 2 (at predose) and on Day 15 (prior to discharge), 1 PK sample will be taken at 24 hours postdose. Predose PK samples will also be obtained on Days 3, 5, and 8. If applicable, a sample will be collected at the ED visit. PK sample collection times are provided as a guidance and may be modified based on clinical needs. Actual dates and times of sample collection must be recorded. The following time intervals are proposed: predose samples may be obtained between waking up and dosing. Postdose samples may be obtained within $\pm 5\%$ of the scheduled collection time. Post-assay remaining PK plasma samples may be stored for metabolite identification.

Study Schedule Protocol J2D-MC-CVAA: Part B (MAD)-Cohort 8

	S	Treatment/In CRU											Post treatment	ED ^a
Study Day	≤28	-1 1 2 3 5 8 14 15 16 17 18											23	
Visit Window (days)													±2	
Visits	1 ^b	2											3	
CRU admission		X												
CRU discharge												X		

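### SAP Table 4 times every Part B sample from the Day 1 dose, so Day 14 tmax and the superimposed Day 1/Day 14 profiles cannot be produced correctly as written

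*SAP*

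**What the plan says.** SAP Section 9.2.3, Table 4, defines two assessment-time variables. Scheduled time is "Time in hours of the assessment relative to the planned time of the first drug administration per period". Actual time is "Actual time in hours calculated as the sampling data/time minus the date/time of the first drug administration per period". No variable for time since the most recent dose is defined anywhere in the SAP.

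The table in SAP Section 6.2 gives Cohorts 7, 8 and 9 one period each; Cohort 7, for example, is planned as "100 mg LY3526318 or Placebo QD" under Period 1 only. The Part B schedules in SAP Appendix 2 add: "Study drug will be administered once daily in the CRU through Day 14, and the exact time of administration will be recorded".

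SAP Section 16.2.2 then requires: "Actual sampling times will be used in all computations involving sampling times". It lets scheduled time stand in when an actual time or a dose time is missing, but does not say which dose is meant.

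The Day 14 outputs that depend on a clock are:
- tmax, ticked for MAD Day 14 in Table 6 (Section 16.1.1.2) with no reference dose named, and a Part B secondary endpoint in Section 5.0, Table 2;
- AUC0-24,ss, defined in Table 6 as the area across one 24-hour dosing interval at steady state and computed as AUCtau, with the area at the nominal 24-hour point as fallback;
- the Part B mean plots in Section 16.2.1, where "geometric mean profiles will be presented for all treatments in a single plot with a Day 1 and Day 14 profiles superimposed".

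**The concern.** Resetting the clock at each period suits the Part A crossover cohorts, where each period has one dose. It does not suit repeated dosing within one period. In Part B the first dose of the period is always the Day 1 dose, yet a Day 14 profile has to be timed from the Day 14 dose.

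At stake are one Part B secondary endpoint (Day 14 tmax), the Day 14 profile figures, and the fallback for AUC0-24,ss. Two clocks are needed, because the trough plot in Section 16.2.1 runs continuously from Day 1 and is served correctly by time since first dose. Only that clock is specified.

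**Working it through.** **Inputs**
- Clock origin: first dose of the period (SAP Table 4).
- Periods in Part B: one (SAP Section 6.2).
- Doses: once daily, Days 1 to 14 (SAP Appendix 2).
- Sampling on Days 1 and 14: "PK samples will be collected at time zero (predose) and at approximately at 1, 2, 4, 6, 8, and 12 hours after dosing", plus a 24-h sample on Days 2 and 15, where the Day 2 sample is the predose sample. Further predose samples are taken on Days 3, 5 and 8. Cohorts 8 and 9 have three later samples after Day 15.

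**Check that the schedule is read correctly.** Protocol Appendix 5 gives 19 PK samples for Cohort 7 and 22 for Cohorts 8 and 9.
- Cohort 7: 7 (Day 1) + 4 (Days 2, 3, 5, 8) + 8 (Day 14 through 24 h) = 19.
- Cohorts 8 and 9: 7 + 4 + 7 + 4 = 22.

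Both agree.

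**Day 14 on the Table 4 clock.** The nominal offset is 13 × 24 = 312 h.

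| Hours since Day 14 dose | 0 | 1 | 2 | 4 | 6 | 8 | 12 | 24 |
|---|---|---|---|---|---|---|---|---|
| Hours on Table 4 clock | 312 | 313 | 314 | 316 | 318 | 320 | 324 | 336 |

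**Consequences**
1. tmax: a peak at 1 to 12 h after the Day 14 dose is reported at 312 + 1 = 313 h to 312 + 12 = 324 h.
2. Superimposed profiles: Day 1 occupies 0 to 24 h and Day 14 occupies 312 to 336 h, so the curves do not overlap.
3. Fallback for AUC0-24,ss: on this clock the nominal 24-h sample is the Day 2 predose sample, not the Day 15 sample.

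**What does not change.** Every Day 14 time in a participant's profile moves by the same constant s. The area depends only on concentrations and differences between times: (t2 + s) − (t1 + s) = t2 − t1. Lambda-z is a slope and is unchanged by s; half-life follows from it; Cmax is a concentration.

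An illustration used a one-compartment oral curve with the SAP's linear-up/log-down rule. The absorption rate (0.7/h) and half-lives are assumptions, because the documents give no human half-life.

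| Assumed half-life (h) | Day 14 interval AUC, dose clock | Day 14 interval AUC, Table 4 clock | tmax, dose clock (h) | tmax, Table 4 clock (h) |
|---|---|---|---|---|
| 4 | 5.666 | 5.666 | 2 | 314 |
| 12 | 17.207 | 17.207 | 4 | 316 |
| 24 | 34.518 | 34.518 | 4 | 316 |
| 48 | 68.594 | 68.594 | 4 | 316 |

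Lambda-z was also identical on both clocks. Of AUC, Cmax and tmax, only tmax moves.

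**The case against.** The strongest reply is that the SAP plainly intends a dose-relative clock on Day 14. Table 4 lists common variables, while the PK rules sit in Section 16. Table 6 has its own MAD Day 14 column, and its 24-hour fallback makes sense only if nominal time restarts at the Day 14 dose. Section 16.2.1 superimposes the two days and Section 16.2.2 mentions a dose time. The Part B table shell in Appendix 4 gives Day 14 tmax one digit before the decimal point, not three. A tmax near 313 h would be seen at once.

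Most of this stands, and it lowers the practical risk. It does not correct the definition. It shows that Section 16 and Appendix 4 contradict Table 4, which remains the only place where actual time is defined.

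Two stronger readings are tempting, and the documents do not support them.

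- A reader might infer that AUC0-24,ss is also wrong, and with it the accumulation ratio, Day 14 CL/F and the MAD dose-proportionality model. Table 6 ties AUC0-24,ss to the steady-state dosing interval through AUCtau, and a constant shift leaves that area unchanged. Only the fallback, used when AUCtau is missing, is exposed.
- A reader might expect the error to be patched by subtracting a nominal 312 h, and then put a size on the remaining timing and AUC error. The protocol says "In Part B, all doses will be administered at the CRU approximately between 08:00 AM and 11:00 AM", so the Day 14 dose could fall 309 to 315 h after the Day 1 dose. But neither document proposes that subtraction, exact dose times are recorded, and actual times are required. Any AUC percentage built on it would rest on a repair the plan does not contain.

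**Conclusion.** Wrong as written, minor severity. Table 4 states a rule that, applied with Section 16.2.2, puts Day 14 tmax about 312 h too high, prevents the superimposed profiles and misdirects the 24-hour fallback for AUC0-24,ss. This is more than missing detail, because the stated rule gives the wrong answer for a secondary endpoint.

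The effect stops there. Cmax, lambda-z and half-life are unaffected. So is AUC0-24,ss, provided AUCtau is taken from the Day 14 dose as Table 6 implies; accumulation, Day 14 CL/F and dose proportionality then stand as well. The 312-h figure is nominal, and the actual offset follows each participant's recorded dose times. The conclusions about tmax, the plots and the fallback need no pharmacokinetic assumption; the assumed half-lives only illustrate that the area does not move.

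**What to change.** In SAP Table 4:
1. Keep scheduled and actual time since the first dose of the period, and state that in Part B it serves the trough-versus-time plot.
2. Add scheduled and actual time since the recorded profile dose. The reference is the Day 1 dose for the Day 1 profile through its 24-h sample, and the Day 14 dose for samples from Day 14 to Day 19. The Day 14 predose sample is the 0-h point.
3. State in Section 16.2.2 and Table 6 that the added variable is used for Day 14 tmax, profile plots, AUCtau and the 24-hour fallback.

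Use the recorded Day 14 dose time, not a fixed nominal offset.

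The cost is a few lines of SAP text and one added pair of derived times in the PK concentration dataset. Dose and sample times are already recorded, so no new data are needed.
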